16 STUDY MANAGEMENT

16.1 Investigator Responsibilities

16.1.1 Investigator Agreement

Each Investigator will provide the Sponsor a copy of his/her current curriculum vitae and a signed Investigator Agreement, prior to initiation of the study.

16.1.2 Institutional Review Board

The IRB or other committee functioning in a similar capacity will review and approve the protocol and any protocol amendments, initial and revised informed consent (IC) documents, and recruitment materials, if applicable. After approval by the IRB, documentation of approval and the approved IC document will be sent to Terumo BCT before any subject is enrolled into this study.

16.1.3 Informed Consent

The Investigator is responsible for preparing the written IC document for this study. Terumo BCT will provide the Investigator an IC template. The Investigator may rearrange or reword the contents of the template, or may add other elements or language, provided the meaning and content are not changed or deleted.

Prior to subject participation in this study, the Investigator must obtain written IRB approval for the protocol and the ICF. The approved consent form will clearly reflect the IRB approval date.

Once the subject's initial eligibility has been determined, the Investigator or person designated by the Investigator, who has been trained on the protocol, will explain the nature and scope of the study, potential risks and benefits of participation, answer questions for the subject and ask the subject to participate in the study. The study will be explained to the study subject in lay terms, in their native language in a quiet, non-disruptive setting. Potential subjects will be given as much time and privacy as necessary to review the informed consent prior to agreeing to participate in the study. Additionally, if the subject desires, they can take a copy of the consent with them so that they can discuss potential participation with others outside the study team. If the subject agrees to participate, the subject has read the ICF, and has had all of their questions answered, then the ICF must be signed and personally dated by the subject and the person completing the consent process. A copy of the signed and dated ICF will be provided to the study subject.

All subjects are free to withdraw from participation in this study at any time, for any reason(s), specified or unspecified, and without prejudice. The reason(s) for the subject discontinuing or terminating from the study must be recorded on the eCRF.

16.1.4 Study Files and Record Retention

Investigational sites will maintain all records pertaining to this study for a minimum of 2 years following pre-market approval or 2 years after the study is discontinued. The sponsor will notify investigational sites of the discontinuation. Prior to discarding any study-related records, all clinical sites must contact the sponsor for direction.

16.1.5 Regulatory Compliance

Sites are responsible for meeting all applicable FDA regulations (eg, 21 CFR 600-680 and 21 CFR 800) and AABB standards. Sites will be responsible for staying current on new standards and meeting any new regulations which may be implemented during the course of this study.

16.2 Sponsor Responsibilities

16.2.1 Amendments to the Clinical Investigation Plan

Any amendment to the protocol, as deemed appropriate by Terumo BCT, will be implemented as the study progresses. Amendments will be submitted to the IRB for written approval, before implementation.

16.2.2 General Responsibilities

As per ISO 14155 Section 8 and 21 CFR 812, Terumo BCT is responsible for selecting qualified Investigators and providing them with the information they need to conduct the investigation properly, ensuring quality study conduct and proper monitoring of the investigation, ensuring required approvals are obtained and that significant new information about an investigation is promptly reported to reviewing IRB/EC and government authorities as well as annual reports as required.

16.3 Joint Investigator-Sponsor Responsibilities

16.3.1 Training

The Sponsor will train applicable study team members as to the device, protocol, and study procedures and will provide updated information as it becomes available during the course of the study, if applicable. The Investigator is responsible for ensuring that additional site personnel that were not trained by the Sponsor receive applicable documents and training.

16.4 Collecting and Recording Data

The Investigators will maintain complete, accurate, legible, and easily retrievable data, and will allow personnel authorized by Terumo BCT access to all study data at any time. Such data shall also be secured in order to prevent loss of data.

All required data for this study will be recorded from the source documentation onto standardized eCRFs.

16.4.1 Source Documents

Source data is all information, original records of clinical observations, or other activities in a clinical trial necessary for the reconstruction and evaluation of that trial. Source data are contained in source documents. Examples of these original documents and data records include Blood Center records, evaluation checklists, and laboratory results.

16.4.2 Case Report Forms

The study eCRF via EDC is the primary data collection instrument for the study. All data must be recorded in English. Any missing data must be explained.

Completed eCRFs will be reviewed and signed by the Investigator. The CRA will verify the EDC data with the subject's source data, evaluate the data for accuracy, consistency, and completeness, and will ensure that all forms with missing data and/or errors are ultimately addressed. Accurate and complete eCRFs for a subject must be completed in a timely manner.

16.5 Protocol Compliance

The Investigator is responsible for ensuring the study is conducted in accordance with the procedures and evaluations described in this protocol

16.6 Termination of the Study

For reasonable cause, either the Investigator or the Sponsor may terminate the Investigator's participation in this study, provided a written notice is submitted within the time period provided for in the Clinical Trial Agreement (CTA). In addition, Terumo BCT may terminate the study at any time upon immediate notice for any reason, including but not limited to, Terumo BCT's belief that termination is necessary for the safety of subjects or failure to meet the primary endpoints.

16.7 Publication Policy

Terumo BCT recognizes the importance of communication of medical study data, and encourages the publication of such data in reputable scientific journals and the presentation of such data at scientific seminars and conferences. Any proposed publication or presentation of the data generated from the study must be provided to Terumo BCT for timely review in accordance with the terms of the CTA between the Investigator, the Institution, and Terumo BCT. Terumo BCT shall not, in its scientific publications or promotional material, quote from publications by Investigators without full acknowledgment of the source. As this will be a multi-site study, all

Investigators agree not to publish individual site data. All study data will be published as 1 or more manuscripts based on the accumulated data from all study sites.

## **1.0 Introduction**

This statistical analysis plan (SAP) is being developed after review of the protocol CTS-5059 and electronic case report forms (eCRFs). Reference materials for this SAP include the Clinical Investigation Plan (CIP) and the eCRFs.

The purpose of this plan is to prospectively (a priori) outline the types of analyses and presentations of data that will form the basis for conclusions to be reached that will answer the study objectives outlined in the CIP. This plan explains in detail how the data will be handled or analyzed, adhering to commonly accepted standards and practices of biostatistical analysis in the medical device industry.

The overall objective of this study will be achieved through descriptive analyses involving the device efficiency and safety variables collected in this study. All variables will be reported in listing format. All variables specified in this SAP will be analyzed and presented in descriptive tabulations and selected variables will be summarized and compared with criteria in FDA Guidance for Industry on Collection of Platelets by Automated Methods. The study objectives will be explored through the pre-specified primary, secondary, and safety endpoints.

This document contains information to support the generation of a Clinical Investigation Report (CIR) for Clinical Protocol CTS-5059, including detailed descriptions of the statistical methodologies to be applied, as well as the in-text tables, analysis summary tables, subject data listings, and descriptive graphics intended to present the analysis results.

The planned analyses identified in this SAP may be included in regulatory submissions and/or future manuscripts. Exploratory analyses, not identified in this SAP, may be performed to support the clinical development program. Any post-hoc, or unplanned, analyses that are performed but not identified in this SAP will be clearly identified in the CIR. The structure and content of this SAP provides sufficient detail to meet the requirements identified by the FDA and International Conference on Harmonisation of Technical Requirements for Registration of Pharmaceuticals for Human Use (ICH): Guidance on Statistical Principles in Clinical Trials.

## **2.0 Study Objectives**

The objective of this study is to verify that platelets collected on the Trima Accel System, Version 7.0 and stored in Platelet Additive Solution (PAS) meet the FDA requirements for leukoreduction.

## **3.0 Statistical Methodology**

All statistical analyses will be performed using SAS® software version 9.3. All testing and/or confidence intervals will be at a significance level of 0.05 unless stated otherwise.

### **3.1 Sample Size**

As specified in the FDA guidance, for up to 1 allowed failure, 93 platelet products are required to show that the proportion of platelet units with an acceptable residual WBC level is at least 95% with 95% confidence. With 93 platelet products being collected, 16 failures

or less is required to show that the proportion of platelet units with an acceptable platelet yield is at least 75% with 95% confidence.

Up to 450 healthy adult subjects will be enrolled in this study to complete 279 procedures (93 single, 93 double, and 93 triple platelet products).

### 3.2 Study Populations

Analysis populations for this clinical investigation will be the Full Analysis Set (FAS) and Safety Populations.

For all analyses by platelet product, the platelet product type (single, double, triple, or unassigned) will be determined from the calculated platelet yield (see Section 3.3) using the following.

- If the platelet yield, rounded to the nearest tenth, is  $\geq 9.3 \times 10^{11}$ , then the product will be analyzed as a triple.
- Otherwise, if the platelet yield, rounded to the nearest tenth, is  $\geq 6.2 \times 10^{11}$ , then the product will be analyzed as a double.
- Otherwise, if the platelet yield, rounded to the nearest tenth, is  $< 6.2 \times 10^{11}$ , then the product will be analyzed as a single.
- Otherwise, if the procedure was not started, not completed or the platelet yield could not be determined for some other reason, as per the protocol analysis exclusion criteria, then the subject will be analyzed as “Unassigned”.

The Safety Population will include all subjects enrolled in this trial for whom at least 1 apheresis procedure is initiated. A procedure will be considered to have been initiated if a Trima procedure start date and time are present. The Safety Population will be used for all summaries except the primary and secondary endpoints and the derived apheresis related parameters.

Due to the design of the study, a given subject may be enrolled in the study on multiple occasions. These subjects may also qualify for the Safety Population more than once. If this occurs, the subjects will be analyzed separately for each enrollment.

The Full Analysis Set (FAS) will be defined separately for single, double, and triple platelet products and will not include any repeat subjects. The FAS for a given platelet product will consist of all collections that do not meet any of the exclusion criteria specified below. The FAS will be used to examine the primary and secondary endpoints and the derived apheresis related parameters.

Data points will be excluded from the FAS analysis in the following situations:

1. Inability to collect a complete unit due to:
  - a. Subject issues (inadequate access, reaction, needle abort, procedure disqualification upon Trima Accel device update of subject platelet count and hemoglobin or hematocrit).
  - b. Decision to stop procedure by subject, Investigator, nursing staff or operator.

- c. Equipment failure or malfunction (unrecoverable system failure; plugged or malfunctioning filter[s]).
  - d. Protocol deviation.
2. Decision to stop the procedure due to a change in the subject platelet count (i.e. subject qualifies for double, however day-of platelet count is for a single platelet product and 93 single platelet products have already been collected).
  3. Failure or inability to update the Trima Accel system with the actual platelet count (platelet count performed on sample taken from Trima Disposable sample pouch) AND the actual platelet count differs from the entered platelet count by more than 10%. Updating the Trima Accel system with actual platelet count from the sample pouch is standard procedure for the Trima Accel system.
  4. Incomplete or incorrect collection procedure or post-collection processing due to:
    - a. Equipment failure or malfunction.
    - b. Subject issues (inadequate access, reaction, needle abort).
    - c. Unanticipated centrifuge stop during collection procedure.
    - d. Failure to follow post-collection handling procedure outlined in the Trima Operator's Manual, and supplement(s).
    - e. Subject and procedure samples are not taken as specified in protocol.
    - f. Solution other than InterSol added to platelets prior to storage.
    - g. Results of endpoint assays are not available.

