Intended Use:	The Trima Accel system is an automated blood cell separator intended for use in collecting blood components for later transfusion into patients.
Study Centers Planned:	At least 2 and up to 8 Blood Centers in the United States
Objective:	To verify that platelets collected on the Trima Accel system with Version 7.0 software enhancements and stored in PAS meet the FDA requirements for leukoreduction ($< 5.0 \times 10^6$ residual white blood cells [WBC] per transfusable unit).
Rationale:	The study is designed to evaluate changes to the Trima Accel software to ensure the modified software meets the FDA acceptance criteria for leukoreduction and platelet yield. The operating range for the system flow rates, anticoagulant ratios, storage conditions, and centrifugal forces are the same as the currently cleared Trima Accel system. There are no changes to the environment or storage conditions for platelets; therefore, no in vitro or in vivo platelet quality data will be collected.
Outcome Measures:	
Primary Endpoint: The proportion of platelet units with an acceptable residual WBC level. Acceptable residual WBC counts are: singles = residual WBC level $< 5.0 \times 10^6$; doubles = residual WBC level $< 8.0 \times 10^6$ or $< 5.0 \times 10^6$ for each transfusable unit; and triples = residual WBC level $< 12.0 \times 10^6$ or $< 5.0 \times 10^6$ for each transfusable unit.
 
Secondary Endpoint: The proportion of platelet units with an acceptable platelet yield. Acceptable platelet yield for single, double and triple platelet products are: platelet yield $\geq 3.0 \times 10^{11}$ for singles, platelet yield $\geq 6.2 \times 10^{11}$ for doubles, and platelet yield $\geq 9.3 \times 10^{11}$ for triples.

Safety Measures:	Safety will be monitored through collection of adverse events (AEs), serious adverse events (SAEs), and unanticipated adverse device effects (UADEs).
Inclusion Criteria:	
 1. Age 18 years or older. 2. Meets the inclusion criteria defined by the Blood Center for an apheresis platelet with PAS collection on the Trima Accel system. These criteria are based on FDA guidance and American Association of Blood Banks (AABB) standards. Note: subjects who are deferred from volunteer community donations because of travel restrictions, piercings, or tattoos may participate in the study, as products are not transfused. 3. Has given written informed consent.

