7.2 Secondary Endpoint

The proportion of platelet units with an acceptable platelet yield. Acceptable platelet yield for single, double and triple platelet products are presented in Table 7-2.

Table 7-2: Secondary Endpoint Acceptance Criteria

Parameter	Measured	Acceptance Criteria ^a
Platelet yield – Single Unit	Platelet concentration \times volume	Platelet yield is $\geq 3.0 \times 10^{11}$
Platelet yield – Double Unit	Platelet concentration \times volume	Platelet yield is $\geq 6.2 \times 10^{11}$
Platelet yield – Triple Unit	Platelet concentration \times volume	Platelet yield is $\geq 9.3 \times 10^{11}$

^a These yields represent typical lab minimums for splitting into double and triple platelet products.

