8 INVESTIGATIONAL PLAN

8.1 Study Design

This is a prospective, open-label, multi-center controlled study to evaluate the leukoreduction of platelets stored in PAS collected on the Trima Accel system with Version 7.0 software enhancements. Up to 450 healthy adult subjects will be enrolled in this study to ensure 93 single, 93 double, and 93 triple platelet product evaluable data points. Evaluable is defined as a completed platelet product that does not meet any of the protocol analysis exclusion criteria (Section 15.4).

The additional subjects account for screen failures, incomplete procedures, and protocol analysis exclusions.

Concurrent plasma will be collected from qualifying subjects to exercise the platelet/plasma product combination. Of the 93 evaluable procedures required for each type (singles, doubles, and triples) at least 25% of collections will include concurrent plasma collection. The Trima Accel system calculates subject eligibility for blood product combinations based on platelet count, hemoglobin or hematocrit, and total blood volume (TBV) of the subject.

Red blood cells will not be collected in this study; platelets will be collected in 65% InterSol PAS and 35% plasma. The Trima Accel system collects RBCs after platelets and plasma, therefore there is no effect of RBC collections on the platelet collections due to platelet collection software modifications. Similarly, there is no effect of the platelet collections on subsequent RBC collections.

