### 3.4 Primary Endpoints

- Proportion of platelet units with an acceptable residual WBC level for single platelet products.
- Proportion of platelet units with an acceptable residual WBC level for double platelet products.
- Proportion of platelet units with an acceptable residual WBC level for triple platelet products.

The acceptable residual WBC level is defined as following:

For single platelet products: residual white blood cell measurement, rounded to the nearest tenth,  $< 5.0 \times 10^6$ .

For double platelet products:

- Parent container has a residual white blood cell measurement, rounded to the nearest tenth,  $< 8.0 \times 10^6$ ,
- If not met, each component residual white blood cell measurement, rounded to the nearest tenth,  $< 5.0 \times 10^6$ .

For triple platelet products:

- Parent container has a residual white blood cell measurement, rounded to the nearest tenth,  $< 12.0 \times 10^6$ ,
- If not met, each component residual white blood cell measurement, rounded to the nearest tenth,  $< 5.0 \times 10^6$ .

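### SAP 3.2 sets the product group, and so the primary residual WBC limit, from measured yield instead of the product the procedure was run to collect, so an over-yielding collection gets a looser limit

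*SAP*

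**What the plan says.** The protocol synopsis states the objective as fewer than 5.0 x10^6 "residual white blood cells [WBC] per transfusable unit". Protocol Table 7-1 gives parent limits of <5.0, <8.0 and <12.0 x10^6 for singles, doubles and triples. Doubles and triples may alternatively pass if each component is <5.0 x10^6.

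SAP 3.2 decides which of these limits applies: "For all analyses by platelet product, the platelet product type (single, double, triple, or unassigned) will be determined from the calculated platelet yield". At a rounded yield of 9.3 x10^11 or more, "then the product will be analyzed as a triple"; from 6.2 up to that point it is a double, and below 6.2 a single. SAP 3.4 then tests doubles and triples in sequence. The first step is "Parent container has a residual white blood cell measurement, rounded to the nearest tenth", below 8.0 or 12.0 x10^6. The second is "If not met, each component residual white blood cell measurement, rounded to the nearest tenth", below 5.0 x10^6. Singles have no component step.

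Protocol 8.1 has product type starting from the donor: the device "calculates subject eligibility for blood product combinations based on platelet count", with hemoglobin or hematocrit and total blood volume. Protocol 10.2.2 updates the device with the day-of counts before collection. Neither section reclassifies a product by its yield afterwards. The only text linking yield to division is the footnote to Table 7-2, repeated in SAP 3.7.3: "These yields represent typical lab minimums for splitting into double and triple platelet products".

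**The concern.** The 8.0 and 12.0 x10^6 parent limits serve a per-unit objective of 5.0 x10^6 because the contents will be shared between two or three units. If the limit follows yield, a bag with many platelets earns a higher WBC allowance whether or not it was meant to become, or did become, that many units. Once the parent passes, no component is examined, so a unit above the stated figure could be counted as a success.

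The protocol's own secondary endpoint shows that product type and yield are separate there. It plans for up to 16 of 93 doubles, or of 93 triples, falling below the yield criterion, which is possible only if a product remains a double or triple whatever it yields. The SAP would move those products to another group with another WBC limit.

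The primary conclusion for each product type is at stake, because the pass rule leaves no room for a misjudged product.

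**Working it through.** **1. The plan's own figure.** Inputs: 93 products per type with at most 1 failure (protocol 15.1, SAP 3.1), and a one-sided 95% Clopper-Pearson lower limit that must exceed 95% (SAP 3.7.3). The lower limit with f failures in n is the 5th percentile of a Beta(n - f, f + 1) distribution.

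- n = 93, f = 1: 95.001%, a pass. Equivalently, the chance of at most 1 failure at a true failure rate of 5% is 0.95^93 + 93 x 0.05 x 0.95^92 = 0.0500.
- n = 93, f = 2: 93.4%, a fail.
- 93 is the smallest n that passes with one failure.

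The stated sample size is reproduced. One product moved from failure to success can reverse a group's conclusion.

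**2. When the parent limits protect the unit.** On an even split, 8.0/2 = 4.0 and 12.0/3 = 4.0 x10^6 per unit. Both are below 5.0, provided two or three units are made.

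**3. When yield raises the group but not the number of units.** After rounding to a tenth, the highest passing parent values are 7.9 (double limit) and 11.9 (triple limit). WBC values are x10^6 and yields x10^11.

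| Run as | Measured yield | Parent limit for type run | Parent limit under SAP | Units made | Highest WBC per unit that passes |
|---|---|---|---|---|---|
| Single | 6.2 to 9.2 | <5.0 | <8.0 | 1 | 7.9 / 1 = 7.9 |
| Double | 9.3 or more | <8.0 | <12.0 | 2 | 11.9 / 2 = 5.95 |

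**4. The range that matters.** For the undivided single, it is a parent count of 5.0 to 7.9. For the two-unit double, it is narrower than the change of limit suggests. A parent of 8.0 to 9.9, split evenly, gives 4.0 to 4.95 per unit and would pass Table 7-1 through its component alternative. Only parents of 10.0 to 11.9 put both units at 5.0 or above. An uneven split could put one unit over 5.0 at a lower parent count.

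**5. When the extra unit is made.** A double yielding 9.3 or more and divided into three gives at most 11.9/3 = 3.97 per unit. A single yielding 6.2 or more and divided into two gives at most 7.9/2 = 3.95. The per-unit objective is then met on an even split.

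**6. The opposite direction.** A collection run as a double but yielding below 6.2 is judged as a single: below 5.0 in total, with no component step. A parent of 6.0 split into 3.0 and 3.0 would fail although both units meet the objective.

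**The case against.** The strongest reply is that a false pass needs three things together: a yield above the type's range, a high WBC count, and fewer units than the yield class implies. If sites divide whenever the yield reaches 6.2 or 9.3 x10^11, as the footnote suggests is typical, yield class and unit count agree and the per-unit problem disappears. High counts also look rare. Protocol 5.1 reports 99.9% of hyperconcentrated products below 1.1 x10^6 per dose for the modified algorithm alone (log-normal regression), and all 24 products below 5.0 x10^6 when it was combined with other Version 7.0 changes. This stands as an argument about frequency. It does not remove the gap, because the footnote describes typical practice and requires no division, and SAP 3.4 does not check that a division took place.

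A reader might infer three stronger things that the documents do not support:

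- That protocol 10.3 fixes the number of units. It lists reasons for termination, including a donor qualifying for a type whose target is full. It does not say how a bag is divided afterwards.
- That sites and the analysis will apply conflicting limits to the same bag, for example a triple collection yielding 9.0 x10^11. No section gives sites an acceptance decision or lets them skip component counts. The SAP treats this product as a double, with a stricter parent limit, so this case does not hide a unit above 5.0 x10^6.
- That the limit can simply be read from the count of Products A, B and C. SAP 3.3 lists these only where applicable, and SAP 3.4 uses them as a fallback. If they were filled in only after a parent failure, a double or triple whose parent passed would look like one unit and be wrongly held to 5.0 x10^6.

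**Conclusion.** The point holds as a flaw in how the primary limit is assigned. Measured yield can loosen the limit from <5.0 to <8.0, or from <8.0 to <12.0 x10^6, relative to the product the procedure was run to collect. Where no extra unit is made, a passing collection can contain one unit at 7.9 x10^6, or two at 5.95 x10^6 each on an even split.

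It would be wrong to conclude that the SAP is expected to pass units above the limit with any regularity. The documents do not allow the frequency to be computed, and what they report suggests it is low. The point still deserves correction because it affects the primary endpoint, departs from the protocol's use of product type, and meets a rule under which one failure in 93 passes and two fail. The per-unit figures assume an even split and the SAP's rounding to a tenth.

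**What to change.** In SAP 3.2 and 3.4 together, assign the analysis group and the WBC limit by the product type the procedure was run to collect after the day-of platelet count update, not by measured yield. Protocol 10.2.2 already has Trima procedure details recorded. The sponsor should confirm that they identify the type run, since the eCRF is not among the documents. Changing SAP 3.4 alone would leave the groups of SAP 3.2 with mixed limits inside one binomial proportion.

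Where component records show fewer units than the type run, apply the limit for the number of units made, or require each unit to be <5.0 x10^6. Absent component records should not be read as one unit. Keep the yield-based grouping as a sensitivity analysis.

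The cost is SAP wording and one derivation. A few products will face a stricter limit, and group sizes may shift slightly. Sizes should be checked after regrouping: with one failure, the lower limit is 95.05% at 94 products but 94.95% at 92, so a group that fell to 92 could no longer absorb a failure.
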